Adipose-derived Stromal Vascular Fraction Injections to Stimulate Hair Regrowth for Androgenetic Alopecia

PROTOCOL: GIDAA-01 Rev: D

Study Sponsor: The GID Group, Inc.
[name]
[name]

Sponsor Contact Director of Clinical Affairs

Date: March 24, 2016

The study will be conducted in accordance with the design and specific provisions of this IRB approved protocol, in accordance with the ethical principles that have their origin in the Declaration of Helsinki, and that are consistent with Good Clinical Practice (GCP) and the applicable regulatory requirement(s). The Principal Investigator will assure that no deviation from, or changes to; the protocol will take place without prior agreement from the sponsor and documented approval from the IRB, except where necessary to eliminate an immediate hazard(s) to the trial participants. The Principal Investigator will promptly report to the IRB and the sponsor any changes in research activity and all unanticipated problems involving risk to human subjects, or others.

I have read and agree to follow the procedures as outlined in this protocol.

Signature of Investigator

Date

SUMMARY

Objectives: The general objective of this study is to conduct a safety and feasibility study of a single injection of autologous adipose-derived SVF for the treatment of alopecia.

Specific Objectives

1. Safety - Adverse Events
2. Feasibility – Pre-op to post-op hair density (number of hairs per square centimeter) and hair thickness

Design: This is a prospective, non-randomized, non-blinded, interventional, consecutive series, multiple site study to determine initial safety and feasibility of a single injection of autologous adipose-derived SVF for the treatment of alopecia.

Subject Population:

1. Males and females 18 - 60 years of age that have been diagnosed with androgenetic alopecia.
2. Subjects will be in good health (ASA Class I-II) with a BMI < 35.
3. Must have at least a 2cm x 2cm spot on the scalp which shows evidence of alopecia without scarring or traumatic injury
4. Able and willing to make the required study visits.
5. Able and willing to give consent and follow study instructions.
6. Must speak, read and understand English

Exclusion Criteria:

1. History of bleeding disorders, anticoagulation therapy that cannot be stopped 14 days prior to injection
2. Allergic to lidocaine, epinephrine, valium or sodium phosphate
3. Individuals with a propensity for keloids
4. Individuals with diminished decision-making capacity will not be included in this research study.
5. Current use of anti-inflammatory or anticoagulation medications that affect bleeding or are for bleeding disorders. These include: Plavix, Warfarin (Coumadin, Jantoven, Marfarin).
6. Use of concomitant treatments, including topical medications, oral medications, meso-therapy, non-ablative fractional laser treatment, low-level laser therapy, interfollicular PRP injection and hair transplantation within the preceding 6 months.
7. All smokers and other tobacco users.

| | |
|------------------------------------|---|
| Subject | Subjects will be recruited from the practice of the Principal Investigator (PI) at each site and/or other colleagues and healthcare professionals in the community. Recruitment will be prospective for this study. Subjects will be recruited via; 1) email utilizing a list of patients that have given their prior consent to be contacted in this manner 2) at the PI's office when they come in for their regularly scheduled appointments or 3) referrals from healthcare professionals within the community or 4) via IRB approved flyers. |
| Investigational Sites | Up to 3 sites |
| Estimated Total Sample Size | Eight (8) subjects will be recruited to participate in the study. This study is a small pilot safety and feasibility study not requiring sample size. |
| Plan for Data Analysis: | Adverse events will be recorded. Hair density (hairs per square centimeter) and hair thickness will be compared pre and post treatment. |

Table of Contents

| | | |
|--------|---|----|
| 1 | Introduction | 6 |
| 2 | Study Objectives | 6 |
| 3 | Study Design..... | 6 |
| 4 | Study Population..... | 7 |
| 4.1 | Subjects..... | 7 |
| 4.1.1 | Inclusion Criteria | 7 |
| 4.1.2 | Exclusion Criteria..... | 7 |
| 4.2 | Study Site Selection..... | 7 |
| 4.3 | Concomitant Medications..... | 7 |
| 5 | Study Visits and Methods | 9 |
| 5.1 | Study Measurements..... | 9 |
| 5.1.1 | Safety | 9 |
| 5.1.2 | Feasibility | 9 |
| 5.2 | Study Visit and Procedures | 9 |
| 5.2.1 | Visits..... | 9 |
| 5.2.2 | Recruitment | 10 |
| 5.2.3 | Informed Consent & HIPAA..... | 10 |
| 5.2.4 | Enrollment..... | 11 |
| 5.2.5 | Study Timeline..... | 11 |
| 5.2.6 | Methods..... | 11 |
| 5.2.7 | Adverse Events..... | 12 |
| 5.2.8 | Data Collection..... | 12 |
| 5.2.9 | Case Report Forms..... | 12 |
| 5.2.10 | Data Management and Quality Control..... | 12 |
| 5.3 | Subject Exit and Study Completion Procedures..... | 13 |
| 5.3.1 | Subject Exit Status..... | 13 |
| 5.3.2 | Completed Study..... | 13 |
| 6 | Side Effects, Adverse Events and Other Risks..... | 13 |
| 7 | Statistical Analysis..... | 14 |

| | | |
|-----|---|----|
| 7.1 | Sample Size | 14 |
| 7.2 | Statistical Methods | 14 |
| 7.3 | Procedure for Accounting for Missing, Unused or Spurious Data | 14 |
| 8 | Ethical and Regulatory Considerations | 14 |
| 8.1 | Institutional Review Board..... | 14 |
| 8.2 | Protocol Reviews..... | 14 |
| 8.3 | Protocol Amendments | 15 |
| 8.4 | Subject Information and Informed Consent | 15 |
| 8.5 | Study monitoring | 15 |
| 8.6 | Additional Considerations..... | 15 |
| 9 | References | 16 |

1 Introduction

Androgenetic alopecia (AGA) is the most common form of hair loss and affects 50% and 23% of Caucasian men and women, respectively, over the age of 50. The percentage of men and women affected over the age of 70 increases to 80% and 60% of Caucasian men and women, respectively^{1,2}. Although alopecia is considered a minor dermatologic condition, it is seen as a serious condition with major life consequences by those with alopecia and has been associated with increased incidence of myocardial infarction, hypertension and hypercholesterolaemia³⁻⁴. Androgenetic alopecia is associated with feelings of anxiety, depression and various personality disorders among men and women due to physical appearance³⁻⁶. Depression, anxiety, aggressiveness, impaired quality of life and social inadequacy have been documented. The presence of alopecia in women is particularly stressful^{5,7}.

Human Clinical Studies

Two studies have recently been published that used adipose-derived SVF cells for hair regrowth in humans and have found it to be safe and effective. Shin et al retrospectively examined 27 women who received 12 injections (one injection per week) of adipose-derived SVF for treatment of alopecia⁸. After 12 weeks hair density and thickness significantly increased with no adverse events reported.

Fukuoka et al reported on 2 groups of patients with alopecia⁹. One group had 11 men and 11 women that were treated with 6 injections spaced every 3 to 5 weeks of adipose-derived SVF and monitored for up to 7 months. They found a significant increase in hair growth and reported no adverse events or safety issues. In the second group 10 patients (8 men and 2 women) were treated on one side with adipose-derived SVF and the other with placebo (saline). Patients were blinded to the treatment. This group also received 6 injections similar to the other group. The treatment group had significantly more hair growth than the control side.

A hair regeneration procedure that is less invasive than surgical hair transplantation, entails less risk than current surgical treatments, and is less time consuming would benefit men and women with alopecia.

2 Study Objectives

The general objective of this study is to conduct a safety and feasibility study of a single injection of autologous adipose-derived SVF for the treatment of alopecia.

3 Study Design

This is a prospective, non-randomized, non-blinded, interventional, consecutive series, multiple site study to determine initial safety and feasibility of a single injection of autologous adipose-derived SVF for the treatment of alopecia.

4 Study Population

4.1 Subjects

A total number of eight (8) subjects from a single population, i.e., patients who have been diagnosed with androgenetic alopecia, will be recruited.

4.1.1 Inclusion Criteria

1. Males and females 18 – 60 years of age and older that have been diagnosed with androgenetic alopecia.
2. Subjects will be in good health (ASA Class I-II) with a BMI < 35.
3. Must have at least a 2cm x 2cm spot on the scalp which shows evidence of alopecia without scarring or traumatic injury
4. Able and willing to make the required study visits.
5. Able and willing to give consent and follow study instructions.
6. Must speak, read and understand English

4.1.2 Exclusion Criteria

1. History of bleeding disorders, anticoagulation therapy that cannot be stopped 14 days prior to injection
2. Allergic to lidocaine, epinephrine, valium or sodium phosphate
3. Individuals with a propensity for keloids
4. Individuals with diminished decision-making capacity will not be included in this research study
5. Current use of anti-inflammatory or anticoagulation medications that affect bleeding or are for bleeding disorders. These include: Plavix, Warfarin (Coumadin, Jantoven, Marfarin). In addition, if any of the following medicines are used two (2) weeks prior to surgery the patient will be ineligible.
6. Use of concomitant treatments, including topical medications, oral medications, meso-therapy, non-ablative fractional laser treatment, low-level laser therapy, interfollicular PRP injection and hair transplantation within the preceding 6 months.
7. All smokers and other tobacco users.

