4.3 Concomitant Medications

If the subject is taking any medications on this list, it should be discontinued two (2) weeks prior to surgery, and only Tylenol should be taken for pain. All other medications must be

specifically cleared by the doctor prior to surgery. It is absolutely necessary that all current medications be specifically cleared by the doctor and the nursing staff.

| | |
|--|---|
| ADVIL | CP-2 TABLETS |
| ALCOHOL | DARVON WITH ASA PULVULES |
| ALEVE | DARVON COMPOUND PULVULES |
| ALKA SELTZER (EFFERVESCENT Tablet) | DARVON COMPOUND 65 |
| ALKA SELTZER (COLD MEDICINE Tablet) | DARVON N WITH ASA |
| ANACIN TABLETS AND CAPLETS (MAXIMUM STRENGTH) | DASIN CAPSULES |
| ARTHRALGEN TABLETS | DAYPRO |
| ARTHRITIS STRENGTH BUFFERIN TABS | DINOL TABLETS |
| ARTHROPAN LIQUID | DISALCID CAPSULES |
| ARTHROTEC | DOAN'S PILLS |
| ASA TABLETS ENSEALS | DUOPRIN'S SYRUP |
| ASPIRIN WITH CODEINE | DUOPRIN CAPS |
| ASPIRIN TABLETS | DURADYNE TABLETS |
| ASPIRIN AD TABLETS | DYNOSAL TABLETS |
| ASPIRIN EXTRA STRENGTH | EASPRIN |
| ASPIRBUF TABLETS | ECOTRIN TABLETS |
| ASPERGUM | EFFICIN TABLETS |
| AXOTAL TABLETS | EFFICIN WITH CODEINE TABLETS |
| BAYER ASPIRIN TABLETS | EQUAGESIC TABLETS |
| BAYER CHILDREN'S COLD TABLETS | EXCEDRIN TABLETS AND CAPS |
| BAYER CHILDREN'S ASPIRIN TABLETS | EASPRIN |
| BC TABLET AND POWDER | ECOTRIN TABLETS |
| BUFF-A COMP #3 TABLETS WITH CODEINE | FENOPROFEN |
| BUFFAPRIN TABLETS | FIORINAL TABLETS |
| BUFFERIN TABLETS | FIORINAL WITH CODEINE |
| BUFFERIN ARTHRITIS STRENGTH TABLETS | FOUR-WAY COLD TABLETS |
| BUFFERIN EXTRA-STRENGTH TABLETS | GAYSAL-S TABLETS |
| BUFFERIN WITH CODEINE #3 TABLETS | GEMISIN TABLETS |
| BUFFETS II TABLETS | GOODY'S HEADACHE POWDER |
| BUF-TABS | HYDROCODONE (VICODIN, LORTAB, NORCO) |
| CAMA ARTHRITIS PAIN RELIEVER | IBUPROFEN |
| CELEBREX | INDOMETHACIN |
| CODEINE | INDOCIN |
| CONGESPRIN CHEWABLE TABLETS | INDO-LEMMON CAPSULES |
| COPE TABLETS | LANORINAL TABLETS |
| COSPRIN TABLETS | MAGAN TABLETS |
| COUMADIN | MAGSAL TABLETS |
| | MARNAL CAPS |
| | MAXIMUM BAYER ASPIRIN |
| | MEASURIN TABLETS |
| | MEDIPREN |
| | MEFENAMIC ACID |
| | MIDOL CAPLETS |

| | |
|-------------------------------------|--------------------------------------|
| METHOCARBAMOL WITH ASPIRIN TABLETS | PIROXICAM (FELDENE) |
| MECLOMEN | PLAVIX |
| MECLOFENAMATE | ROBAXISAL TABLETS |
| MICRAININ TABLETS | RUFEN |
| MOBDIN TABLETS | S-A-C TABLETS |
| MOBGESIC TABLETS | ST. JOESPH ASAPIRIN FOR CHILDREN |

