| MOMENTUM MUSCULAR BACKACHE | ST. JOESPH COLD TABLETS FOR CHILDREN |
| MOTRIN, FORMULA TABLETS | SINE-OFF SINUS MEDICINE TABLETS |
| NALFON | SK-65 COMPOUND CAPS |
| NAPROSYN | STANBACK TABLETS AND POWDER |
| NAPROXEN | SUPAC CAPS |
| NEOCYLATE TABLETS | SYNALGOS CAPS |
| NORGESIC & NORGESIC FORTE TABLETS | SYNALGOS-DC CAPSULES |
| NUPRIN | TALWIN COMPOUND TABLETS |
| ORUDIS | TRENDAR |
| OS-CAL GESIC TABLETS | TOLECTIN |
| PABLATE | TRIAMINICIN TABLETS |
| PABLATE-SF TABLETS | TRIGSESIC |
| PEPTO BISMOL TABLETS AND SUSPENSION | TRILISATE TABLETS & LIQUID |
| PERCODAN & PERCODAN-ASA DEMI TABLET | ULTRAM |
| PERSISTIN TABLETS | URACEL |
| PLAVIX | VANQUISH |
| PROPOXYPHENE COMPOUND 65 | VERIN |
| | VITAMINE SUPPLEMENT |
| | VOLTAREN |
| | ZORPRIN TABLETS |

5 Study Visits and Methods

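### Exclusion item 5 bars current use of Plavix or warfarin without dating it, while item 1 and section 4.3 imply that a patient may stop these drugs two weeks before surgery and enter

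*Combined protocol and SAP*

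**What the plan says.** Four pieces of text govern these drugs.

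- Section 4.1.2, item 5, first sentence, excludes "Current use of anti-inflammatory or anticoagulation medications that affect bleeding or are for bleeding disorders. These include: Plavix, Warfarin (Coumadin, Jantoven, Marfarin". No visit or date is attached.
- Item 5, second sentence, adds that "if any of the following medicines are used two (2) weeks prior to surgery the patient will be ineligible". No list follows it; the only medication list is in 4.3.
- Section 4.1.2, item 1, excludes "anticoagulation therapy that cannot be stopped 14 days prior to injection", together with a history of bleeding disorders.
- Section 4.3 instructs: "If the subject is taking any medications on this list, it should be discontinued two (2) weeks prior to surgery". The list contains Coumadin once ("COUMADIN | MAGSAL TABLETS") and Plavix twice ("MECLOMEN | PLAVIX" and "PLAVIX | VANQUISH").

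Section 4.3 also has a general safeguard: "It is absolutely necessary that all current medications be specifically cleared by the doctor and the nursing staff". The Summary repeats item 1 and the first part of item 5, but omits item 5's two-week sentence.

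**The concern.** Item 5 reads as a bar on anyone taking warfarin or Plavix. Item 1 and 4.3 read as if such a person may come off the drug and enter. Because *current* is undated, a site has to choose between them.

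Two things are at stake. The first is consistency. With up to three sites, one may exclude the patient at screening and leave the treatment alone, while another stops the treatment and enrols the same kind of patient. The second is safety, which is the first specific objective of the study. Stopping a prescribed antithrombotic exposes the subject to the clotting risk for which it was prescribed, here in order to enter a hair-regrowth pilot. Section 6 does not mention this; it says that nothing is needed beyond the precautions for standard liposuction and scalp injection.

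**Working it through.** The plan states no figure on this point, so the check sets the texts side by side and adds a short timeline.

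**1. Coverage.** Item 5 names two drugs, Plavix and warfarin (the latter with three brand names). Both are on the 4.3 stop list: Coumadin 1 entry + Plavix 2 entries = 3 entries, covering 2 of 2 drugs. The overlap is therefore complete at drug level.

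**2. Two readings of *current*.**

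| Reading | Item 5 | Item 1 clause and the three 4.3 entries | Patient on warfarin at screening who could stop |
|---|---|---|---|
| Judged at screening | Excludes | No use: the patient is already out | Excluded |
| Judged over the 14 days before surgery | Does not exclude once the drug is stopped | Consistent with item 5 | Stops the drug and may enter |

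On the second reading the dates line up. Item 1 counts 14 days from injection, 4.3 counts two weeks from surgery, and 5.2.6 puts surgery and injection on the same day. The second sentence of item 5 does not settle which reading is meant. It is introduced as an additional condition, so it does not date the first sentence.

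**3. Can status at screening and at surgery differ?** Section 5.2.2 has eligibility screened in the office or by phone. Section 5.2.5 gives 0 to 14 days from first contact to consent and expects surgery to be set within two to four weeks.

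- Assumption A, the two to four weeks run from consent: first contact to surgery is 0 + 14 = 14 days at the shortest and 14 + 28 = 42 days at the longest. The latest stop day is surgery minus 14, which is day 0 to day 28 after first contact. This is never earlier than the day of consent.
- Assumption B, they run from first contact: 14 to 28 days, with latest stop day 0 to 14. Here a 14-day stop after consent fits only if consent comes at least 14 days before surgery.

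Under A on every schedule, and under B on some, a patient taking warfarin at phone screening can be 14 days off it at surgery. The two readings then give opposite eligibility decisions.

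**4. Safeguards in the text.** Apart from the timing and the general clearance in 4.3, nothing in the document requires the prescriber's agreement to stop these drugs or says when to restart them.

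**The case against.** The strongest reply is that there is no conflict. The 14-day reading reconciles every clause, and the rival reading leaves item 1's anticoagulation clause and three list entries with no purpose, which is a reason to reject it. This stands as far as it goes: a reader might infer that the protocol flatly contradicts itself, and the text does not support that. Exclusion criteria are also cumulative, so item 1 admits nobody by itself. But reconciling the clauses confirms the other half of the concern, because the protocol then does provide for stopping a prescribed antithrombotic in order to enter.

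A reader might also infer that subjects could reach surgery while on warfarin or Plavix. The documents do not support this either: on both readings nobody should. The exposure at issue is withdrawal of treatment, not operative bleeding.

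Nor is the protocol silent on safeguards. All medications must be cleared, liposuction follows standard practice, and site procedures and the separate procedure consents, which are not among the documents, may cover prescriber contact and restarting. That is a partial answer. The clearance names neither the prescriber nor the risk of stopping, and whether such patients may enter at all should be settled in 4.1.2 whatever those papers say.

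Staff training and sponsor monitoring may limit differences between sites. However, under 5.2.8 each investigator trains his or her own staff on the protocol, and its text leaves the question open.

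Finally, a smaller edit would be to define *current* as within 14 days of surgery and to add prescriber agreement and a restart plan. That is workable and keeps what may be the sponsor's intent. In a pilot of eight subjects, exclusion is simpler and removes the withdrawal risk.

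**Conclusion.** The point holds in this form: item 5 is undated, the texts agree only on the 14-day reading, and on that reading a prescribed antithrombotic is stopped for an elective pilot with only general clearance by the doctor and nursing staff.

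It is a low-frequency issue. The documents give no rate of use, and entry is limited to ages 18 to 60 and ASA I-II, so few candidates should be affected. The case for acting is that the harm to one subject could be serious and the correction is cheap. The timeline rests on the reading of 5.2.5 stated above. The safety argument assumes that anyone prescribed these drugs takes them for a thrombotic risk. No efficacy analysis changes, and nothing here bears on the choice of eight subjects.

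**What to change.** Amend 4.1.2, 4.3 and the Summary together.

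1. Exclude anyone taking a prescribed anticoagulant (warfarin under any name included) or Plavix at screening or at any time from 14 days before screening through the day of surgery. State that such treatment will not be stopped for this study. The window matters: a rule judged only at screening would miss someone who stopped just before it, or who started during the weeks before surgery.
2. In item 1, keep the history of bleeding disorders and put this rule in place of the clause about anticoagulation that cannot be stopped.
3. In 4.3, state that use of Coumadin or Plavix makes the patient ineligible, instead of directing that they be discontinued.
4. In item 5, move anti-inflammatory drugs to the two-week rule and make its second sentence refer explicitly to the list in 4.3. Carry the same sentence into the Summary.

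Optional detail: for aspirin taken on prescription, which stays on the 4.3 list, ask for the prescriber's agreement and a restart date.

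The cost is a wording amendment with IRB approval. The few candidates on these drugs must be replaced to reach eight subjects; their number cannot be estimated from the documents.

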4.2 Study Site Selection

A maximum of three sites will participate in clinical data collection. The subjects will be divided equally among the sites as much as possible.

4.3 Concomitant Medications

If the subject is taking any medications on this list, it should be discontinued two (2) weeks prior to surgery, and only Tylenol should be taken for pain. All other medications must be

specifically cleared by the doctor prior to surgery. It is absolutely necessary that all current medications be specifically cleared by the doctor and the nursing staff.

| | |
|--|---|
| ADVIL | CP-2 TABLETS |
| ALCOHOL | DARVON WITH ASA PULVULES |
| ALEVE | DARVON COMPOUND PULVULES |
| ALKA SELTZER (EFFERVESCENT Tablet) | DARVON COMPOUND 65 |
| ALKA SELTZER (COLD MEDICINE Tablet) | DARVON N WITH ASA |
| ANACIN TABLETS AND CAPLETS (MAXIMUM STRENGTH) | DASIN CAPSULES |
| ARTHRALGEN TABLETS | DAYPRO |
| ARTHRITIS STRENGTH BUFFERIN TABS | DINOL TABLETS |
| ARTHROPAN LIQUID | DISALCID CAPSULES |
| ARTHROTEC | DOAN'S PILLS |
| ASA TABLETS ENSEALS | DUOPRIN'S SYRUP |
| ASPIRIN WITH CODEINE | DUOPRIN CAPS |
| ASPIRIN TABLETS | DURADYNE TABLETS |
| ASPIRIN AD TABLETS | DYNOSAL TABLETS |
| ASPIRIN EXTRA STRENGTH | EASPRIN |
| ASPIRBUF TABLETS | ECOTRIN TABLETS |
| ASPERGUM | EFFICIN TABLETS |
| AXOTAL TABLETS | EFFICIN WITH CODEINE TABLETS |
| BAYER ASPIRIN TABLETS | EQUAGESIC TABLETS |
| BAYER CHILDREN'S COLD TABLETS | EXCEDRIN TABLETS AND CAPS |
| BAYER CHILDREN'S ASPIRIN TABLETS | EASPRIN |
| BC TABLET AND POWDER | ECOTRIN TABLETS |
| BUFF-A COMP #3 TABLETS WITH CODEINE | FENOPROFEN |
| BUFFAPRIN TABLETS | FIORINAL TABLETS |
| BUFFERIN TABLETS | FIORINAL WITH CODEINE |
| BUFFERIN ARTHRITIS STRENGTH TABLETS | FOUR-WAY COLD TABLETS |
| BUFFERIN EXTRA-STRENGTH TABLETS | GAYSAL-S TABLETS |
| BUFFERIN WITH CODEINE #3 TABLETS | GEMISIN TABLETS |
| BUFFETS II TABLETS | GOODY'S HEADACHE POWDER |
| BUF-TABS | HYDROCODONE (VICODIN, LORTAB, NORCO) |
| CAMA ARTHRITIS PAIN RELIEVER | IBUPROFEN |
| CELEBREX | INDOMETHACIN |
| CODEINE | INDOCIN |
| CONGESPRIN CHEWABLE TABLETS | INDO-LEMMON CAPSULES |
| COPE TABLETS | LANORINAL TABLETS |
| COSPRIN TABLETS | MAGAN TABLETS |
| COUMADIN | MAGSAL TABLETS |
| | MARNAL CAPS |
| | MAXIMUM BAYER ASPIRIN |
| | MEASURIN TABLETS |
| | MEDIPREN |
| | MEFENAMIC ACID |
| | MIDOL CAPLETS |

| | |
|-------------------------------------|--------------------------------------|
| METHOCARBAMOL WITH ASPIRIN TABLETS | PIROXICAM (FELDENE) |
| MECLOMEN | PLAVIX |
| MECLOFENAMATE | ROBAXISAL TABLETS |
| MICRAININ TABLETS | RUFEN |
| MOBDIN TABLETS | S-A-C TABLETS |
| MOBGESIC TABLETS | ST. JOESPH ASAPIRIN FOR CHILDREN |
| MOMENTUM MUSCULAR BACKACHE | ST. JOESPH COLD TABLETS FOR CHILDREN |
| MOTRIN, FORMULA TABLETS | SINE-OFF SINUS MEDICINE TABLETS |
| NALFON | SK-65 COMPOUND CAPS |
| NAPROSYN | STANBACK TABLETS AND POWDER |
| NAPROXEN | SUPAC CAPS |
| NEOCYLATE TABLETS | SYNALGOS CAPS |
| NORGESIC & NORGESIC FORTE TABLETS | SYNALGOS-DC CAPSULES |
| NUPRIN | TALWIN COMPOUND TABLETS |
| ORUDIS | TRENDAR |
| OS-CAL GESIC TABLETS | TOLECTIN |
| PABLATE | TRIAMINICIN TABLETS |
| PABLATE-SF TABLETS | TRIGSESIC |
| PEPTO BISMOL TABLETS AND SUSPENSION | TRILISATE TABLETS & LIQUID |
| PERCODAN & PERCODAN-ASA DEMI TABLET | ULTRAM |
| PERSISTIN TABLETS | URACEL |
| PLAVIX | VANQUISH |
| PROPOXYPHENE COMPOUND 65 | VERIN |
| | VITAMINE SUPPLEMENT |
| | VOLTAREN |
| | ZORPRIN TABLETS |

5 Study Visits and Methods

